## 6. Sample Size and Power Considerations

The primary objective of the study is to demonstrate a statistically significant difference between the active treatments and placebo.

This study is expected to enroll 50 subjects in each of the three treatment arms, for a total of 150 randomized subjects. Assuming a 10% drop out rate, 45 subjects per group are expected to complete the study.

Assuming a common standard deviation in the change from baseline for the pre-CAE® inferior corneal fluorescein staining of 0.72 units, a sample size of 45 subjects per group will have 90% power to detect a difference of 0.5 units between each of the active treatment groups and the placebo group using a two-sample t-test at a significance level of 0.05. A sample size of 45 subjects per treatment arm will have 90% power to detect a mean difference of 0.80 units in the change from baseline for the pre-CAE® ocular discomfort as assessed by the Ora Calibra® Ocular Discomfort Scale, assuming a standard deviation of 1.15 units. Using an analysis of covariance model (ANCOVA) for each primary

endpoint should yield standard deviations no greater than those from a two-sample t-test. Therefore, the power for each endpoint for both the sign and the symptom is 81%, assuming independence between the endpoints. The power for both the sign and the symptom in both active treatments is 66%, assuming independence of treatments.

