### 9.4 Data Analysis Conventions

All data analysis will be performed by SDC after the study is completed and the database has been locked and released for unmasking. Statistical programming and analyses will be performed using SAS® Version 9.4 or higher. Output will be provided in RTF (Rich Text Format) for tables and PDF (Portable Document Format) for tables, listings, and figures using landscape orientation. All study data will be listed by subject, treatment, and visit (as applicable) based on all enrolled subjects unless otherwise specified.

All summaries will be presented by treatment group and visit where appropriate, unless otherwise specified. Summaries will be provided for demographics, baseline medical history, concurrent therapies, and subject disposition. For the purpose of summarization, medical history, concurrent therapies, and adverse events will be coded to Medical Dictionary for Regulatory Activities (MedDRA) and World Health Organization (WHO) Drug dictionaries, as appropriate.

Summaries for continuous and ordinal variables will include the number of observations (n), arithmetic mean, standard deviation (SD), median, minimum, and maximum. Minima and maxima will be reported with the same precision as the raw values; means and medians will be presented to one additional decimal place than reported in the raw values. Standard deviations will be presented to two additional decimal places than reported in the raw values. Summaries for discrete variables will include frequency counts and percentages. All percentages will be rounded to one decimal place (i.e., XX.X%).

All statistical tests will be two-sided with a significance level of 0.05 ( $\alpha = 0.05$ ) unless otherwise specified. Confidence intervals (CI) for differences between treatment groups will be two-sided at 95% confidence levels where appropriate. All p-values will be rounded to four decimal places; p-values

less than 0.0001 will be presented as "<0.0001"; p-values greater than 0.9999 will be presented as ">0.9999".

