### 15.6 Immunogenicity to HL036 in Serum

Analyses of immunogenicity data will be conducted as ad-hoc analyses. The anticipated ad-hoc analyses of immunogenicity are as follows.

Immunogenicity will be summarized using discrete summary statistics. Counts and proportions of patients with anti-drug antibodies (ADA) will be presented by visit and treatment group. Exact 95% Clopper-Pearson confidence intervals will be presented. Treatment groups will be compared using Fisher's Exact Test, and exact 95% confidence intervals for the pairwise proportion differences will be constructed.

Antibody titer of patients positive for ADA will be summarized using continuous descriptive statistics and presented by visit and treatment group. Treatment groups will be compared using two-sample t-tests. The differences in means, two-sided 95% confidence intervals (CIs) for the difference in means and p-values will be reported. Wilcoxon rank sum tests will also be conducted.

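### Anti-drug antibody titres are compared as differences in arithmetic means with no log scale named; if they are dilution titres, the reported effect and its interval are unreliable

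*SAP*

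**What the plan says.** Serum immunogenicity is a safety measure in both documents (protocol 6.2, SAP 3.3), sampled at Visits 2, 4, 5 and 6. For titre, SAP 15.6 says: "Antibody titer of patients positive for ADA will be summarized using continuous descriptive statistics and presented by visit and treatment group". The comparison follows: "Treatment groups will be compared using two-sample t-tests". The output is specified too: "The differences in means, two-sided 95% confidence intervals (CIs) for the difference in means and p-values will be reported". A rank test is added: "Wilcoxon rank sum tests will also be conducted".

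SAP 9.4 fixes the content of a continuous summary: "Summaries for continuous and ordinal variables will include the number of observations (n), arithmetic mean, standard deviation (SD), median, minimum, and maximum". Geometric means, log titres and titre ratios appear in neither document.

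The standing of the analysis is also clear: "Analyses of immunogenicity data will be conducted as ad-hoc analyses". Protocol 10.4.7 plans only counts and proportions for immunogenicity. The SAP's table list has no titre table, and its only immunogenicity listing is of blood draws.

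**The concern.** A titre is usually the last dilution at which a sample still reacts, so titres move by factors (10, 20, 40, 80 and so on) and differences between arms are fold-changes. On that scale one high responder can carry most of an arm's arithmetic mean and most of its SD. The difference in means then largely reflects the highest one or two subjects, and the t interval around it rests on a normal approximation that a small, strongly skewed sample does not support.

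At stake is the only planned between-arm effect estimate for antibody level. A reader comparing the two concentrations would take the size of any titre difference, and its uncertainty, from that estimate and its interval. The Wilcoxon test gives a p-value but neither of these.

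**Working it through.** **Inputs from the documents.** Arithmetic mean and SD (SAP 9.4); t-test and difference in means with 95% interval (SAP 15.6); two-sided 0.05 (SAP 9.4); at most about 50 subjects per arm (SAP 6). The documents give no titre, no expected number of positives and no assay description, so there is no planned figure to reproduce.

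**Assumptions.** Two-fold dilution titres starting at 10; log2 titre roughly normal; SD of 1 to 2.5 doublings; 5 to 25 positives per arm; true difference 4-fold (2 doublings).

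**Step 1: a worked example with 10 positives per arm.** Nine titres are shared: 10, 20, 20, 40, 40, 80, 80, 160, 160 (sum 610; in doublings above 10, the sum is 20).

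- Arm A, tenth titre 320 (5 doublings): arithmetic mean (610 + 320)/10 = 93; geometric mean 10 × 2^(25/10) = 57; median 60.
- Arm B, tenth titre 5120 (9 doublings): arithmetic mean (610 + 5120)/10 = 573; geometric mean 10 × 2^(29/10) = 75; median 60. The one top titre is 5120/5730 = 89% of the arm's total.
- Arm C, every titre of arm A times 4: arithmetic mean 372; geometric mean 226; median 240.

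B against C on the raw scale: 573 − 372 = +201, so B looks higher (t-test p = 0.70). On the log scale the ratio is 2^(2.9 − 4.5) = 0.33, so B is lower (t-test p = 0.11; Wilcoxon p = 0.04). The planned output would show a positive mean difference beside a Wilcoxon result that points the other way.

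**Step 2: simulation, 10 positives per arm, true 4-fold difference.** Raw interval: d ± t(0.975, 2n − 2) × s × √(2/n), with d the difference in mean titre and s the pooled SD. The log-scale interval uses the same formula on log2 titre and is back-transformed to a ratio. Each interval is judged against its own target: the true difference in arithmetic means, or the true difference in mean log titre.

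| SD (doublings) | Power: raw t | Power: log t | Power: Wilcoxon | Coverage: raw | Coverage: log |
|---|---|---|---|---|---|
| 1.5 | 0.54 | 0.80 | 0.77 | 85% | 95% |
| 2 | 0.25 | 0.55 | 0.51 | 78% | 95% |

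Repeat runs agree to about 0.01. Almost all the raw-scale misses lie on one side, with the whole interval below the true difference. A sample that happens to lack a very high titre understates the mean and the SD together.

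**Step 3: sensitivity to the assumptions.**

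- Type I error of the raw t-test is 1.7% to 4.3% over the grid, against about 5% on the log scale. It is conservative, so false positives are not inflated.
- With 25 positives per arm and SD 1, both t-tests have power above 0.99. With 25 and SD 2, power is 0.62 raw, 0.93 log and 0.92 Wilcoxon.
- With 5 per arm and SD 2, power is 0.11 raw, 0.28 log and 0.22 Wilcoxon.
- With 3 per arm, the smallest exact two-sided Wilcoxon p-value is 2/C(6,3) = 2/20 = 0.10, so that test cannot reach 0.05. The log t-test has power of only 0.23 (SD 1.5) or 0.15 (SD 2).
- Nowhere on the grid of 5 to 25 positives does the log t-test have less power than the raw t-test.
- The top titre's median share of the arm total is 23% to 45% at 10 positives and 12% to 31% at 25. Equal shares would be 10% and 4%.

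**The case against.** The case for leaving the text alone has several parts.

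- **Low standing.** The analysis is ad hoc, goes beyond what the protocol plans, has no listed table, and plays no part in the success rule of SAP 9.5. This is true and limits the importance of the point. Even so, SAP 15.6 writes out the anticipated method, and that is what would be programmed.
- **Robust outputs already planned.** The Wilcoxon test is unchanged by a log transformation, and the median and range will be shown. This stands. A reader might infer from the raw t-test's power (0.54 and 0.25) that a real dose difference would be missed. The documents do not support that, because the plan also runs the Wilcoxon test. Against the plan as written, moving the t-test to the log scale gains 0.80 − 0.77 = 0.03 or 0.55 − 0.51 = 0.04 in power. The protection is weaker below about 10 positives per arm.
- **The scale is inferred.** The arithmetic mean in SAP 9.4 is a general convention, and the protocol's Appendix 2 sends sample handling to a laboratory manual that is not part of these documents. If log titres are delivered, the complaint falls away, although the SAP should then say so. The raw scale remains the plain reading.
- **Numbers of positives are unknown.** This also stands. No antibody rate is given, so few positives cannot be called the expected case. With many positives and little spread the choice of scale hardly affects power, and with three per arm no method helps much.

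One further inference should be resisted. For log-normal titres the arithmetic mean exceeds the geometric mean by exp((s ln 2)²/2), which is 1.7 at s = 1.5 and 2.6 at s = 2. That describes two different summaries and is not in itself an error in the plan.

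**Conclusion.** The point holds as a minor one. As written, titre is compared through arithmetic means, their difference and a t interval. If titres are dilution titres, these outputs are fragile. At an assumed 10 positives per arm with a 4-fold difference, the nominal 95% interval covers about 85% (SD 1.5 doublings) to 78% (SD 2), and a single subject can reverse the sign of the mean difference. The t-test p-value is affected too, through lost power and not through excess false positives.

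The fault does not extend to the antibody-positive counts and proportions, the median, the Wilcoxon test or any efficacy conclusion. The size rests on assumed spread, assumed numbers of positives and an assumed reporting scale, none of which the documents give.

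**What to change.** Amend SAP 15.6 as follows:

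- State the scale on which the laboratory reports titre. If it is a dilution titre, log-transform it before the t-test.
- Replace the difference in means with geometric mean titres by arm and visit, and ratios of geometric means with back-transformed 95% intervals.
- Keep the median, minimum, maximum and Wilcoxon test.
- Label the titre comparison descriptive. Positivity during treatment arises after randomisation, so the arms being compared are no longer the randomised groups.
- List individual titres when an arm has fewer than two positives, since that arm then supplies no SD on either scale. This could happen with placebo.

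The cost is a few lines of text and a small programming change to an analysis not yet in the table list. It needs no extra subjects, samples or visits, and nothing is lost from the present plan.

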8.3 EXAMINATION PROCEDURES

An ICF must be signed and dated by the subject, the PI or designee and witness (if required) before any study-related procedures are performed.

Procedures listed below should be performed in the given order. See **Appendix 2** for details on methodologies and grading systems.

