### 3.3 Safety Variables

The safety variables include the following:

- Incidence and severity of ocular Adverse Events (AE)
- Incidence and severity of non-ocular AEs
- Best-Corrected Visual Acuity (BCVA) at all visits
- Slit-lamp biomicroscopy at all visits
- Drop comfort assessment (Visit 2)
- Intraocular pressure (IOP) (Visits 1 and 6)
- Dilated fundoscopy (Visits 1 and 6)
- Immunogenicity to HL036 in Serum (Visits 2, 4, 5, and 6)

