### **9.2 Missing or Inconclusive Data Handling**

The primary efficacy analyses will be performed using Markov Chain Monte Carlo (MCMC) multiple imputation methodology for missing values. An analysis using observed data only will also be performed for the primary efficacy variables. As additional sensitivity analyses, Last Observation Carried Forward (LOCF) methodology and imputation via pattern mixture models will also be used to impute missing data for the analyses of the primary efficacy variables.

For the LOCF analyses of the primary efficacy variables at Day 57 (Visit 6), the last value from the previous visits will be carried forward, matching pre-CAE® or post-CAE® time points. A pre-CAE® time point will never be imputed for a post-CAE® value, and vice versa.

No secondary efficacy endpoints or safety endpoints will be imputed.

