### 15. Safety Analyses

All safety analyses will be conducted using the Safety population.

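### The titre tests in SAP 15.6 compare only ADA-positive subjects; after dosing these are non-randomized subsets, so the tests do not estimate HL036's effect on antibody titre

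*SAP*

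**What the plan says.** Serum immunogenicity is a listed safety variable, sampled at Visits 2, 4, 5 and 6 (SAP 3.3, Protocol 6.2). SAP 15.6 opens by stating its status: "Analyses of immunogenicity data will be conducted as ad-hoc analyses". It then sets out two comparisons.

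- **Incidence.** Counts and proportions of ADA-positive subjects are given by visit and arm with exact intervals, and "Treatment groups will be compared using Fisher's Exact Test, and exact 95% confidence intervals for the pairwise proportion differences will be constructed". This is not restricted to positives.
- **Titre.** "Antibody titer of patients positive for ADA will be summarized using continuous descriptive statistics and presented by visit and treatment group". Then: "Treatment groups will be compared using two-sample t-tests", with mean differences, 95% CIs, p-values and Wilcoxon rank sum tests.

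The titre paragraph assigns no value to ADA-negative subjects, does not adjust for Visit 2 status, does not separate pre-existing from treatment-emergent antibodies, sets no minimum number of positives, and does not call the comparison conditional or descriptive. Protocol 10.4.7 plans only the incidence analysis; the titre comparison appears only in the SAP. On the data used, SAP 15 says "All safety analyses will be conducted using the Safety population", and SAP 9.2 says "No secondary efficacy endpoints or safety endpoints will be imputed".

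**The concern.** Randomization makes the arms comparable as a whole. It does not make subsets comparable when they are selected on something that treatment can change. The Visit 2 blood draw is listed before the first randomized dose in Protocol 8.3.2, and Protocol 8.3 says "Procedures listed below should be performed in the given order", so positivity at Visit 2 is a baseline characteristic. From Visit 4 on it is an outcome.

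If HL036 induces antibodies, the placebo positives are mainly subjects with background reactivity, while the HL036 positives are a mixture of background and newly induced subjects. A difference in mean titre then reflects the make-up of that mixture. At stake is how a listed safety variable of a protein drug is read: a p-value or confidence interval printed beside titre by arm invites a causal reading that the comparison cannot carry, in either direction.

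**Working it through.** **Inputs from the documents.** Arm size 50, two-sided alpha 0.05 (SAP 6 and 9.4). The arm size is consistent with the plan's own figures: 45/(1 − 0.10) = 50, and 45 per arm gives t-test power of 0.903 for the sign (0.5 units, SD 0.72) and 0.904 for the symptom (0.80 units, SD 1.15), against the stated 90%. The plan has no figure to reproduce for ADA rates or titres.

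**Assumptions.** Background positivity, induced positivity and titre levels are all assumed. Titres are in doublings (log2), SD 1.5. HL036 is taken to leave the titres of background-positive subjects unchanged.

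**Step 1: what the positives-only difference measures.** Let *s* be the share of HL036 positives that are induced, *m_i* the mean log2 titre of induced subjects and *m_b* that of background subjects. The expected HL036 − placebo difference among positives is

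*s* × (*m_i* − *m_b*).

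Its sign is the sign of the titre gap. If the gap is zero, the difference is zero however many subjects HL036 has turned positive.

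**Step 2: a small example.** Placebo has 2/50 positive at log2 titre 6. HL036 has 2/50 background at 6 and 5/50 induced at 3.

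- Positives only: HL036 mean (2×6 + 5×3)/7 = 27/7 = 3.86; placebo 6.00; difference −2.14, which equals (5/7) × (3 − 6).
- All subjects, negatives set to 0: 27/50 = 0.54 against 12/50 = 0.24; difference +0.30.
- Fisher's test, 7/50 against 2/50: p = 0.16.

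The two titre summaries point in opposite directions, and the incidence test is not significant at these counts.

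**Step 3: the 8% / 30% illustration.** Expected positives are 50 × 0.08 = 4 on placebo and 4 + 46 × 0.30 = 17.8 on HL036, so *s* = 13.8/17.8 = 0.775. With induced titres two doublings lower, the expected difference is 0.775 × (−2) = −1.55 doublings. In simulation, about 35% of computable trials show HL036 significantly lower. Fisher's test detects the excess in about 90% of trials, and a rank test on all subjects (negatives lowest) also in about 90%.

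**Step 4: all three directions.** Simulation, 3,000 trials per row, 4% background, 20% induced. The three titre columns are percentages of trials in which the t-test can be computed; the last two columns are percentages of all trials.

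| Mean log2 titre, background / induced | HL036 mean lower | significantly lower | significantly higher | Fisher on incidence | rank test, all subjects |
|---|---|---|---|---|---|
| 6 / 3 | 98.8% | 46.2% | 0% | 74.0% | 79.2% |
| 6 / 6 | 49.3% | 2.4% | 2.7% | 74.7% | 83.6% |
| 4 / 7 | 1.7% | 0% | 46.8% | 75.3% | 88.2% |

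Induction is the same in every row. Only the assumed titre gap changes, and the positives-only result follows it.

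**Step 5: when the t-test cannot be run.** P(fewer than 2 placebo positives) = (1 − p)^50 + 50p(1 − p)^49. At p = 4% this is 0.130 + 0.271 = 0.40. At p = 2% it is 0.364 + 0.372 = 0.74.

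**The case against.** The strongest reply is that the incidence comparison in the same section already gives the randomized answer on whether HL036 induces antibodies. It uses all subjects with a result, the titre paragraph says openly that it concerns positives, and a reader would see the two together. This largely stands. It limits the consequence but does not give the titre p-values a valid interpretation. Incidence can also be weak when events are few: at 10% background, 10% induced and titres 6/3, Fisher's test detects the excess in 15% of trials, while the titre test is significantly lower on HL036 in 20% of computable trials.

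It is also fair that the analysis is ad hoc, that SAP 19 lists no immunogenicity table, and that study success rests only on the coprimary sign and symptom (SAP 9.5). These points bear on priority, not on validity.

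A reader might infer that the test is built to reassure, or that it has almost no ability to show HL036 raising antibodies. The documents do not support that. They give no ADA rates or titres, and if induced titres exceed background by two doublings (4–12% background, 20–60% induced) the t-test rejects in 24–54% of computable trials, with HL036 higher. A reader might also take the restriction to cover only subjects who turned positive during the study. The text says positive, so subjects with pre-existing antibodies are included, and a lower HL036 mean depends on them.

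**Conclusion.** The concern holds in a limited form. At Visits 4, 5 and 6 the t-tests, mean differences, CIs and Wilcoxon tests on titre are conditioned on a post-randomization outcome and do not estimate a treatment effect. Because the cause is the selection of subjects, analysing log titres or ranks within positives does not remove it. The Visit 2 comparison is not affected.

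The direction of any distortion is unknown. A misleadingly low HL036 mean needs some placebo positives and induced titres below background, and neither is documented. The 35% and 90% figures and the table rest wholly on assumed rates; the 40% figure rests only on an assumed 4% background and 50 sampled placebo subjects. The incidence analysis is sound, and no efficacy conclusion or success criterion is touched. The consequence is modest, but the correction is nearly free.

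**What to change.** In SAP 15.6:

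1. Keep Fisher's exact test and the exact CIs on ADA proportions as the between-arm comparison.
2. Present titres among positives descriptively by arm and visit, with the number positive, and drop p-values and between-arm mean differences at the post-dose visits.
3. Only if a titre test is wanted, use a Wilcoxon rank sum test over all Safety-population subjects with a serum result at that visit, with ADA-negative subjects tied at the lowest rank. This is optional: it has many ties, gives no mean titre difference, and adds little beyond the incidence test (about 90% for both in the 8% / 30% illustration).

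The cost is a few sentences of SAP text, with no new data. What is given up is a formal titre contrast among positives, including any contrast between the two doses, which would be conditional in the same way.

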### 16. Interim Analyses

There will be no interim analyses in this study.

### 17. Changes from Protocol-Stated Analyses

There are no changes from the protocol-stated analyses.

### 18. Revision History

Documentation of revision to the SAP will commence after approval of the Final version 1.0.

### 19. Tables

Tables that will be included in the topline delivery are shown in boldface font.

Table Number	Title	Population
--------------	-------	------------

Table Number	Title	Population
TABLE 14.1.1	SUBJECT DISPOSITION	ALL ENROLLED SUBJECTS
TABLE 14.1.2.1	DEMOGRAPHICS ITT POPULATION	ITT
TABLE 14.1.2.2	DEMOGRAPHICS SAFETY POPULATION	SAFETY
TABLE 14.1.3.1	BASELINE DISEASE CHARACTERISTICS (STUDY EYE)	ITT
TABLE 14.1.3.2	OCULAR MEDICAL HISTORY	ITT
TABLE 14.1.3.3	NON-OCULAR MEDICAL HISTORY	ITT
TABLE 14.1.4.1	CONCOMITANT OCULAR MEDICATIONS BY TREATMENT GROUP, DRUG CLASS AND PREFERRED NAME	ITT
TABLE 14.1.4.2	CONCOMITANT NON-OCULAR MEDICATIONS BY TREATMENT GROUP, DRUG CLASS AND PREFERRED NAME	ITT
TABLE 14.2.1.1	PRE-CAE® INFERIOR CORNEAL FLUORESCEIN STAINING (ORA CALIBRA® SCALE)	ITT WITH MCMC
TABLE 14.2.1.2	PRE-CAE® INFERIOR CORNEAL FLUORESCEIN STAINING (ORA CALIBRA® SCALE)	ITT WITH OBSERVED DATA ONLY
TABLE 14.2.1.3	PRE-CAE® INFERIOR CORNEAL FLUORESCEIN STAINING (ORA CALIBRA® SCALE)	ITT WITH LOCF
TABLE 14.2.1.4	PRE-CAE® INFERIOR CORNEAL FLUORESCEIN STAINING (ORA CALIBRA® SCALE)	ITT WITH PMM
TABLE 14.2.1.5	PRE-CAE® INFERIOR CORNEAL FLUORESCEIN STAINING (ORA CALIBRA® SCALE)	PP WITH OBSERVED DATA ONLY
TABLE 14.2.2.1	PRE-CAE® OCULAR DISCOMFORT (ORA CALIBRA® SCALE)	ITT WITH MCMC
TABLE 14.2.2.2	PRE-CAE® OCULAR DISCOMFORT (ORA CALIBRA® SCALE)	ITT WITH OBSERVED DATA ONLY

Table Number	Title	Population
TABLE 14.2.2.3	PRE-CAE® OCULAR DISCOMFORT (ORA CALIBRA® SCALE)	ITT WITH LOCF
TABLE 14.2.2.4	PRE-CAE® OCULAR DISCOMFORT (ORA CALIBRA® SCALE)	ITT WITH PMM
TABLE 14.2.2.5	PRE-CAE® OCULAR DISCOMFORT (ORA CALIBRA® SCALE)	PP WITH OBSERVED DATA ONLY
TABLE 14.2.3.1	FLUORESCEIN CORNEAL AND CONJUNCTIVAL STAINING (ORA CALIBRA® SCALE)	ITT WITH OBSERVED DATA ONLY
TABLE 14.2.3.2	LISSAMINE GREEN CORNEAL AND CONJUNCTIVAL STAINING (ORA CALIBRA® SCALE)	ITT WITH OBSERVED DATA ONLY
TABLE 14.2.3.3	TEAR FILM BREAK-UP TIME	ITT WITH OBSERVED DATA ONLY
TABLE 14.2.3.4	ORA CALIBRA® CONJUNCTIVAL REDNESS SCALE FOR DRY EYE	ITT WITH OBSERVED DATA ONLY
TABLE 14.2.3.5	UNANESTHETIZED SCHIRMER'S TEST	ITT WITH OBSERVED DATA ONLY
TABLE 14.2.3.6	ORA CALIBRA® OCULAR DISCOMFORT SCALE	ITT WITH OBSERVED DATA ONLY
TABLE 14.2.3.7	ORA CALIBRA® OCULAR DISCOMFORT SCALE (DURING CAE®)	ITT WITH OBSERVED DATA ONLY
TABLE 14.2.3.8	ORA CALIBRA® OCULAR DISCOMFORT & 4-SYMPTOM QUESTIONNAIRE FOR DRY EYE	ITT WITH OBSERVED DATA ONLY

Table Number	Title	Population
TABLE 14.2.3.9	ORA CALIBRA® OCULAR DISCOMFORT & 4-SYMPOTM QUESTIONNAIRE FOR DRY EYE (DIARY)	ITT WITH OBSERVED DATA ONLY
TABLE 14.2.3.10	VISUAL ANALOGUE SCALE	ITT WITH OBSERVED DATA ONLY
TABLE 14.2.3.11	OCULAR SURFACE DISEASE INDEX (OSDI)®	ITT WITH OBSERVED DATA ONLY
TABLE 14.2.3.12	ORA CALIBRA® DROP COMFORT SCALE	ITT WITH OBSERVED DATA ONLY
TABLE 14.2.3.13	ORA CALIBRA® DROP COMFORT QUESTIONNAIRE	ITT WITH OBSERVED DATA ONLY
TABLE 14.3.1.1	ADVERSE EVENT SUMMARY	SAFETY
TABLE 14.3.1.2	ALL OCULAR ADVERSE EVENTS	SAFETY
TABLE 14.3.1.3	ALL NON-OCULAR ADVERSE EVENTS	SAFETY
TABLE 14.3.1.4	ALL OCULAR TREATMENT-EMERGENT ADVERSE EVENTS	SAFETY
TABLE 14.3.1.5	ALL NON-OCULAR TREATMENT-EMERGENT ADVERSE EVENTS	SAFETY
TABLE 14.3.1.6	ALL OCULAR TREATMENT-RELATED TREATMENT-EMERGENT ADVERSE EVENTS	SAFETY
TABLE 14.3.1.7	ALL NON-OCULAR TREATMENT-RELATED TREATMENT-EMERGENT ADVERSE EVENTS	SAFETY
TABLE 14.3.1.8	ALL SERIOUS ADVERSE EVENTS	SAFETY
TABLE 14.3.1.9	ALL OCULAR TREATMENT-EMERGENT ADVERSE	SAFETY

Table Number	Title	Population
	EVENTS BY MAXIMAL SEVERITY	
TABLE 14.3.1.10	ALL NON-OCULAR TREATMENT-EMERGENT ADVERSE EVENTS BY MAXIMAL SEVERITY	SAFETY
TABLE 14.3.1.11	ALL OCULAR TREATMENT-EMERGENT ADVERSE EVENTS BY STUDY DAY OF ONSET	SAFETY
TABLE 14.3.1.12	ALL NON-OCULAR TREATMENT-EMERGENT ADVERSE EVENTS BY STUDY DAY OF ONSET	SAFETY
TABLE 14.3.2	BEST CORRECTED VISUAL ACUITY - LOGMAR	SAFETY
TABLE 14.3.3.1	SLIT LAMP BIOMICROSCOPY	SAFETY
TABLE 14.3.3.2	SHIFT IN SLIT LAMP BIOMICROSCOPY	SAFETY
TABLE 14.3.4.1	DILATED FUNDOSCOPY	SAFETY
TABLE 14.3.4.2	SHIFT IN DILATED FUNDOSCOPY	SAFETY
TABLE 14.3.5	INTRAOCULAR PRESSURE	SAFETY
TABLE 14.3.6	COMPLIANCE WITH STUDY DRUG	SAFETY
TABLE 14.3.7	EXPOSURE TO STUDY DRUG	SAFETY

